2. STUDY OBJECTIVE

2.a. Primary Objective: The purpose of this study is to examine the effectiveness of T4C-MI by testing the intervention's ability to engage the study outcomes (aggression, behavioral infractions, administrative segregation).

2.b. Secondary Objective: The secondary objective of this study is to test the ability of intervention to engage the study treatment targets (impulsivity, interpersonal problem solving, and criminal thinking)

3. STUDY DESIGN

This study will engage a pilot effectiveness trial to examine the extent to which T4C-MI impacts its intended targets (mediating mechanisms) and outcomes among prisoners with SMI. The study will use a randomized controlled design to assign participants to one of the two study arms 1) the study intervention (T4C-MI) or 2) Standard Prison Treatment and programming. The study will take place in the North Carolina Prison system and will involve up to four facilities.

3.a. Allocation to Treatment Groups

In this study randomization will take place on site at the prison, which does not allow electronic equipment to be brought into facilities. Therefore, the study team will use a shuffled envelope to randomize participants on site at the prison. The study team will use a table of computer-generated random numbers and block randomization procedures to ensure an equal distribution of subjects to each arm of the study. Study staff will not be blinded to participant condition.

3.b. Study Duration, Enrollment and Number of Subjects

The study will be active for 4 years. Each participant will be involved for 9 months.

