5. STUDY INTERVENTION

This study will have two study arms: The experimental intervention is T4C-MI and the control condition is Standard Prison Treatment and Programming.

5.a. Experimental Intervention

The research intervention is T4C-MI – Thinking for a Change for prisoners with mental illness. This intervention has two components. The first component is Thinking for a Change (T4C)¹, which is an established, manualized intervention shown to be effective at reducing behavioral infractions and time in administrative segregation among prisoners in the general population. T4C is a highly structured, 25-session, manualized intervention that is delivered in a closed-group format to 8-12 people up to twice a week over 12-14 weeks. The intervention curriculum includes three modules: (1) 10 sessions on social skills training that teach participants cognitive skills to interpret and respond positively to social situations that involve potential conflict; (2) 5 sessions on cognitive restructuring activities that teach participants a concrete process for self-reflection that is designed to help individuals identify and correct maladaptive or dysfunctional thought processes, such as anti-social thoughts, feelings, attitudes and beliefs that could lead to criminal activity; and (3) 10 sessions on problem-solving techniques which integrates the skills from the first two modules into a structured problem-solving method that can be used to manage interpersonally challenging situations. More information on this intervention can be found at in the treatment manual²⁶.

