6. STUDY PROCEDURES

Study participants will complete up to four, face to face interviews. The first interview is the screening interview where study eligibility is determined. Participants who meet the study eligibility criteria are enrolled in the study, randomized into one of the two study conditions. People who are randomly assigned to the experimental condition receive the study intervention and those who are randomly assigned to the control condition receive standard prison treatment and programming. All participants who are randomized to either study condition complete three additional follow up interviews: the baseline interview as well as 3- and 6-month interviews. Additionally, administrative data related to behavioral infractions and administrative segregation are collected at the 9-month time point.

6.a Description of Research Procedures

The study procedures are listed below.

All research interviews will take place in private locations in the prison:

First: Recruitment of study subjects will begin the month prior to the initiation of each intervention cycle. Correctional staff at the facility where the intervention is being delivered, will provide the research team with a list of all of the prisoners in their facility who meet the following criteria: a) 18 years and older: b) have mental health issues: c) have at least 1 year remaining on his or her prison sentence: d) do not have any restriction that would preclude the person from being in group gathering spaces within the prison; and e) do not have an intellectual or developmental disability.

Second: Research staff will go to the prison and invite potentially-eligible prisoners to meet with them in a private setting to learn about the study. During this initial meeting, research staff will provide participants with a flyer that describes the study and discuss potential participant's questions. The study flyer and discussions with potential participants will include information about the voluntary nature of the study and will explain that the person's decision about participation has no bearing on the person's criminal or civil cases. The research staff will also explain that the participant can end his or her participation in the study at any time during the recruitment or study process without negative consequences.

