Three: Immediately after completing the recruitment meeting research staff will complete Informed consent with all participants who express interest in participation in the study. This meeting will take place in a private setting in the prison.

Fourth: Research staff will complete a screening interview immediately after the informed consent process with all potential subjects who agree to participate in the study after completing informed consent. The study screening interview will determine whether participants are eligible to participate in the study by screening for mental health diagnoses, criminogenic risk levels, and prior engagement in T4C.

Fifth: At the end of the screening interview potential participants will be informed whether they meet the study eligibility criteria. Participants who are found eligible for the study and agree to participate will be assigned to a study condition. During the RCT phase of the study, participants will be randomized into one of two conditions, the research intervention (T4C-MI) or the control condition (Standard prison treatment and programming). The research staff will randomly assign participants to a study condition by opening a sequentially numbered envelope and discussing the condition assignment with the participant. In order to be sure that interviews are not too long, the screening and baseline interviews will be broken into two separate interviews, conducted at least one day apart from each other. After randomization is complete the research staff will schedule a mutually agreed upon time to return to complete the baseline interview.

Six: Research staff will complete a baseline interview with all study participants. This interview will take place in a private location in the prison. The baseline interview will include a brief assessment of participant's neurocognitive functioning, clinical and criminal justice history, and baseline assessments of treatment targets and study outcomes. The baseline interview will take 60-90 minutes to complete.

Seven: Research staff will complete follow-up interviews with all study participants at 3-, 6 -months after the baseline interview. Each interview is expected to take 30-60 minutes to complete and will be conducted in a private setting in the prison. Participants' outcomes will also be assessed at 9 months post release using administrative data.

6.b Informed Consent

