The potential mediation effects of the proposed primary treatment targets on study outcomes will be explored using structural equation modelling (SEM) and generalized structural equation modelling (GSEM) frameworks to accommodate for variables that are measured both continuously and dichotomously.

9.d. Sample Size and Power

The sample will include up to 112 participants. Given the preliminary nature of this pilot study, our goals are not to fully test our hypotheses nor estimate effect sizes associated with T4C-MI. The main purpose of this R34 is to collect data on available sample size, sample attrition and sample retention and the generation of data and information necessary to conduct comprehensive power calculations for an R01. Nevertheless, here, the likelihood of detecting statistical significance will be increased due to the use of a longitudinal design with up to four measurements per subject on our treatment targets and outcome

measures. Also, our longitudinal design allows for each participant to serve as his/her own historic control, eliminating between-subjects variation and reducing standard errors, which increases power.

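### The plan does not say whether the envelope series are separate by prison, and no analysis includes facility, so chance site imbalance would go unadjusted

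*Combined protocol and SAP*

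**What the plan says.** **Allocation.** Section 3.a states that "randomization will take place on site at the prison", by envelope, and gives equal arm sizes for the study as the only purpose of blocking: "block randomization procedures to ensure an equal distribution of subjects to each arm of the study". Section 6.a adds that staff allocate by "opening a sequentially numbered envelope". Neither section gives a block size or a stratification factor, or says whether one series serves the whole study or each prison has its own. Section 3.a also says that study staff are not blinded to condition.

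**Structure.** The study "will involve up to four facilities" (section 3). Section 6.a ties enrolment to cycles and to the host prison: "Recruitment of study subjects will begin the month prior to the initiation of each intervention cycle", and "Correctional staff at the facility where the intervention is being delivered, will provide the research team with a list" of candidates. The programme "is delivered in a closed-group format to 8-12 people up to twice a week over 12-14 weeks" (section 5.a). Section 5.b leaves decisions about the services in the control condition to prison staff.

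**Analysis.** Section 9.c lists chi-square tests, Mann-Whitney tests and count regressions for infractions and segregation. For aggression it lists t-tests and a mixed model with occasions nested in individuals. No facility or cycle term appears. Section 9.c also says that infractions and segregation are not collected at baseline.

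**The concern.** Two of the three primary outcomes are events that a prison writes up or imposes, and they are taken from its records. The comparator is also whatever each prison provides. Rates of infractions and segregation may therefore differ between prisons for reasons unrelated to treatment. The documents give no site rates, so this is a plausible assumption and not a documented fact.

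If it holds, a prison that happens to contribute more people to one arm shifts the comparison between arms. For infractions and segregation, no baseline value can absorb part of that shift. Site differences that are neither balanced by design nor adjusted for also stay in the error term. That matters for a pilot whose data are meant to feed power calculations for a larger trial (section 9.d).

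**Working it through.** The plan states no balance, alpha, power or effect-size figure, so there is nothing of its own to reproduce.

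**Inputs from the documents.** "The sample will include up to 112 participants" (section 9.d), hence 112/2 = 56 per arm; up to four facilities (section 3); 1:1 blocking with no stated block size (section 3.a).

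**Assumptions.** Four facilities of 28, or unequal facilities of 45, 33, 22 and 12; block sizes of 4, 6 or 8; one study-wide series used either concurrently or prison after prison.

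**1. One series shared by prisons enrolling at the same time (simulation).**
- 4 × 28: at least one prison is split 17:11 or worse (arms differing by 6 or more) in about 65% of trials, and 18:10 or worse in about 37%. Block size makes almost no difference.
- Unequal facilities: some prison has arms differing by 6 or more in about 52 to 55% of trials.

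**2. The same series used prison after prison.** Only the blocks that straddle a change of prison can be incomplete, so the arms in a prison differ by at most one block length *b*. In simulation with *b* = 4, 6 or 8, the largest difference was 4 for 4 × 28 (0 with *b* = 4) and 6 for unequal facilities.

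**3. A separate series for each prison.** The arms in a prison differ by at most *b*/2, which is 2, 3 or 4 people for blocks of 4, 6 or 8.

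**4. What the imbalance costs.** If facility explains a share *r* of outcome variance and is neither balanced nor adjusted for, the standard error of the treatment difference is larger by a factor of about 1/√(1 − *r*):

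| *r* (assumed) | factor | increase in SE |
|---|---|---|
| 0.05 | 1/√0.95 = 1.026 | 2.6% |
| 0.10 | 1/√0.90 = 1.054 | 5.4% |
| 0.20 | 1/√0.80 = 1.118 | 12% |

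**5. The same cost in outcome units.** Assume that 20, 30, 40 and 50% of participants have an infraction in four equal prisons.
- The mean is 35%, and the variance between prisons is (15² + 5² + 5² + 15²)/4 = 125, an SD of 11.2 percentage points.
- Chance site imbalance then moves the arm contrast with an SD of 11.2 × √(1/56 + 1/56) = 11.2 × 0.189 = 2.1 points. It moves it by 4 points or more in roughly 5% of trials.
- The full standard error of the contrast is √(0.35 × 0.65 × 2/56) = 9.0 points.
- Facility's share of variance is 0.0125/(0.35 × 0.65) = 0.055, so this case sits near the first row of the table.

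**6. Predictability of small blocks.** Someone who always guesses the arm with fewer people so far is right, on average, in a share ½ + (2^*b*/C(*b*, *b*/2) − 1)/(2*b*) of allocations. That is 75% for *b* = 2, 71% for 4 and 68% for 6. For an equal mix of blocks of 2 and 4 it is (1.5 + 2.83)/6 = 72%; for 4 and 6 it is (2.83 + 4.10)/10 = 69%.

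**The case against.** The strongest reply is that the plan is silent on this, not wrong. Envelopes opened on site could well be a separate numbered set for each prison, and the wording fits that as well as it fits one shared list. A reader might infer that the investigators chose unstratified blocks; the documents do not say so.

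A reader might also take 65% as the expected state of this trial. It needs four equal prisons enrolling together from one physical series. Section 6.a describes recruitment before each cycle at the facility running it, and the study is active for four years, so enrolment in turn is at least as natural a reading. *Up to four* facilities also allows fewer. With small blocks used in turn, the imbalance is trivial.

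A third tempting inference is that the treatment comparison is biased, or that closed groups will fall outside 8 to 12 members. Randomisation leaves only chance imbalance. Group size depends mainly on how many people a cycle enrols: with 20 people and consecutive blocks of 4, the treated number stays between 8 and 12.

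Finally, sections 9 and 9.d call the results preliminary. That lowers the priority. It does not answer the point, because section 2.a makes effectiveness on these outcomes the primary objective and the missing facility term costs little to add.

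What stands is that the allocation description is incomplete and that the listed analyses would not correct a site imbalance if one arose.

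**Conclusion.** The point holds as an omission of moderate importance. The plan should say how the envelope series are organised, and its analyses should account for facility. Under the least favourable arrangement, a 17:11 split or worse in some prison is more likely than not (about 65%). Under sequential enrolment with small blocks, the arms in a prison differ by at most about one block length. Which applies cannot be told from the documents.

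The consequence is chance imbalance and a standard error about 3 to 5% larger than necessary if facility explains 5 to 10% of outcome variance. It would be about 12% larger at a 20% share. These shares are assumptions. No systematic bias follows.

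**What to change.** **Section 9.c.** Include facility as a fixed effect in the count regressions for infractions and segregation and in the mixed model for aggression. Name these models as the main comparison for the three primary outcomes, with the unadjusted chi-square, Mann-Whitney and t-tests as supporting summaries. The cost is up to three degrees of freedom with four facilities.

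**Section 3.a.** State that each facility has its own blocked, sequentially numbered envelope series. Vary the block sizes, do not go as low as 2, and conceal the sizes from the staff who enrol. Stratifying further by cycle is optional. The cost is a few envelope sets.

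Small blocks carry a trade-off here, because unblinded research staff both recruit and open the envelopes. Varying the block size does not stop someone guessing the under-filled arm: the guess is right about 72% of the time with blocks of 2 and 4, and still about 69% with 4 and 6. The facility term in the analysis is therefore the more important of the two changes, and the strata should be no finer than needed.

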4. RECRUITMENT AND ENROLLMENT OF SUBJECTS

The RCT phase will use convenience sampling techniques to enroll up to 112 participants who meet the study eligibility criteria.

4.a. Study inclusion criteria include:

- (a) aged 18 years or older;
- (b) have a diagnosis of schizophrenia, schizo-affective disorder, psychotic disorder, bipolar disorder or major depressive disorder;

(c) have moderate to high-risk criminogenic risk levels as determined by the Level of Service Inventory; and
(d) have at least one year or more remaining on his or her prison sentence at the time of the screening interview.

4.b. Study exclusion criteria include:

- (a) an intellectual or developmental disability;
- (b) assault precautions or other restrictions that would preclude the person from being in group gathering spaces within the prison where the intervention will take place; and
- (c) participation in T4C in the last 6-months.

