1. BACKGROUND AND RATIONALE

1.a. Background

People with serious mental illnesses (SMI) are overrepresented across the criminal justice system. While incarcerated in prison, people with mental illness (MI) face higher rates of violence and behavioral infractions than the general prison population and experience administrative segregation (isolation) with more frequency and intensity. These experiences substantially increase negative outcomes for prisoners with MI, including exacerbated symptoms of mental illness and trauma. Moreover, following release, more than 60% of people with MI return to custody within three years, creating an incarceration–punishment cycle at great personal and social cost. This cycle clearly underscores an urgent need for interventions designed to reduce levels of aggression, behavioral infractions, and time in isolation among prisoners with MI, with the overall aim of improving outcomes among this population both while incarcerated and after release.

1.b. Study Rationale

Extant research posits that the best predictors and risk factors for criminal activity are the same for people with SMI and those without SMI^{2,3}. These factors, called criminogenic risks, are derived from the Risk Needs Responsivity model (RNR) and include anti-social behavior, anti-social personality, anti-social cognitions, anti-social associates, substance use, family conflict, school or work problems, and lack of pro-social leisure activities^{4–6}. There is evidence that, compared to non-SMI justice-involved persons, justice-involved persons with SMI have higher overall levels of criminogenic risk factors^{7,8} and higher levels of specific criminogenic risk factors such as criminal thinking and criminal attitudes^{9–12}. The growth in our understanding of the nature and extent of criminogenic risk factors among justice-involved persons with SMI has led some experts to suggest that in order to achieve optimal mental health and criminal justice outcomes in this population, mental health services need to include interventions that directly address criminogenic risk factors^{13,14}.

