9. STATISTICAL ANALYSIS

Given the preliminary nature of this study, statistical analyses of our outcomes will not be conclusive; rather we will examine the data for trends across time rather than relying exclusively on tests of statistical significance.

9.a. Primary Outcomes

The primary outcomes of this study are: Aggression, Receipt of Behavioral Infractions, and Time Spent in Administrative Segregation (see Appendix B).

9.b. Secondary Outcomes

The secondary outcomes of this study are those measures listed as Treatment Targets in the conceptual model: Interpersonal Problem Solving, Criminal Attitudes and Associates, and Levels of Impulsivity (see Appendix B).

9.c. Statistical Methods

Treatment Targets and Study Outcomes that are collected via a standardized measure (i.e. Social Problem Solving, Criminal Attitudes and Associates, Impulsivity, and Aggression) are collected at baseline as well as during follow-up periods (see Appendix A). Study Outcomes that are collected via administrative data (i.e. receipt of behavioral infractions and time spent in administrative segregation), however, are not collected as baseline, rather are summed cumulatively over the period extending from the 3-month follow-up period through the 9-month follow-up period.

To examine the impact of T4C-MI on study outcomes that are measured dichotomously and only collected during follow-up periods (i.e. receipt of disciplinary fractions and administrative segregation), we will use chi-square tests to examine between-group differences during the post-test period. To examine between-group post-test differences when these outcomes are measured as counts (i.e. number of behavioral infractions received and days spend in administrative segregation), nonparametric tests will be used to test differences in group medians (e.g. Mann-Whitney Test) and regressions that can accommodate count data (e.g. Poisson, negative binomial) will be employed.

For Treatment Targets and Study Outcomes that are measured continuously and collected at both baseline and follow-up periods (i.e. Social problem solving, impulsivity, criminal attitudes and associates, and aggression), we will use T-tests to examine between-group differences at posttest as well as mixed effects linear models where measurement occasion at level 1 is nested within the individual at level 2.

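### Criminogenic risk is assessed on everyone before randomisation, but section 9.c specifies no use of it for the two primary outcomes that have no baseline value

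*Combined protocol and SAP*

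**What the plan says.** Section 4.a admits people who "have moderate to high-risk criminogenic risk levels as determined by the Level of Service Inventory". Section 6.a places this assessment in the screening interview, which covers "screening for mental health diagnoses, criminogenic risk levels, and prior engagement in T4C". Allocation comes next: "Participants who are found eligible for the study and agree to participate will be assigned to a study condition". The baseline interview comes later still: "After randomization is complete the research staff will schedule a mutually agreed upon time to return to complete the baseline interview". The LSI classification therefore exists for every randomised person and is fixed before the envelope is opened.

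Section 1.b gives the reason for selecting on it: "the best predictors and risk factors for criminal activity are the same for people with SMI and those without SMI", with criminogenic risks named as those factors.

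After screening, the LSI does not appear again. Section 3.a describes "block randomization procedures to ensure an equal distribution of subjects to each arm of the study" and names no stratification factor. Appendices A and B do not list the LSI by name. Section 9 lists no covariate for any analysis.

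Section 9.c says that infractions and segregation are not collected at baseline and are totalled from month 3 to month 9. For their yes/no forms, "we will use chi-square tests to examine between-group differences during the post-test period". For the counts it plans a Mann-Whitney test and a Poisson or negative binomial regression.

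**The concern.** Aggression, the third primary outcome, has a baseline score and a mixed model over repeated measurements. Infractions and segregation have neither: each is a single cumulative total per person. The argument in section 9.d that repeated measurement lets participants act as their own controls does not reach these two outcomes. A prognostic covariate is the other usual way to gain precision, and the trial already holds one.

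The LSI is also a clean candidate. The baseline interview, which records criminal justice history, follows an assignment that staff and participant both know. The LSI classification precedes it.

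At stake are some precision on two of three primary outcomes and some protection against arms that differ by chance in risk mix. Block randomisation balances the number of people per arm, not their risk. There is also a cost for planning: section 9.d says the pilot is meant to supply inputs for the power calculations of a larger trial, and the LSI-outcome association and the adjusted variance are inputs of that kind.

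**Working it through.** The plan gives no power, effect size, event rate or LSI-outcome correlation, so there is no figure of its own to reproduce. The steps below show scale only.

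**Inputs from the documents.** "The sample will include up to 112 participants" (section 9.d) and equal allocation (section 3.a) give at most 56 per arm.

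**Assumed inputs.** LSI-outcome correlation r from 0.1 to 0.5; two-sided alpha 0.05; a standardised effect of 0.5 for the power column.

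**1. Chance imbalance in a continuous LSI score.** The SD of the standardised difference between arms is √(2/56) = 0.189. The 95% range is ±1.96 × 0.189 = ±0.37 SD. The chance of a difference above 0.25 SD is 19%.

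**2. Gain from adjustment (linear approximation).** Variance is multiplied by 1 − r², and the effective sample size is 112/(1 − r²).

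| r | Variance factor | Effective N | Power at d = 0.5 (unadjusted 75.4%) |
|---|---|---|---|
| 0.1 | 0.99 | 113 | 75.8% |
| 0.2 | 0.96 | 117 | 77.0% |
| 0.3 | 0.91 | 123 | 79.2% |
| 0.4 | 0.84 | 133 | 82.3% |
| 0.5 | 0.75 | 149 | 86.3% |

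**3. The same question for counts.** In 1,500 simulated trials per setting (112 people, control mean 1.5, gamma shape 1, rate ratio 0.6, robust Poisson regression), the LSI slope was set per SD on the log-rate scale. All of these values are assumed.

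| Slope | SE of log rate ratio, unadjusted → adjusted | Variance ratio | Power |
|---|---|---|---|
| 0.2 | 0.267 → 0.265 | (0.265/0.267)² = 0.99 | 53.7% → 53.8% |
| 0.4 | 0.290 → 0.283 | (0.283/0.290)² = 0.95 | 44.4% → 48.7% |
| 0.6 | 0.324 → 0.295 | (0.295/0.324)² = 0.83 | 42.6% → 46.4% |

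**4. What an imbalance does to the estimate.** Suppose half the sample is high-risk. The SD of the arm difference in percent high-risk is √(2 × 0.25/56) = 0.0945, or 9.4 points. The 95% limit is 1.96 × 0.0945 = 18.5 points, and the chance of a gap over 10 points is 29%. If high-risk people have twice the infraction rate (assumed), a gap d with no treatment effect gives a rate ratio of (1.5 + d/2)/(1.5 − d/2):
- at one SD, 1.547/1.453 = 1.065;
- at the 95% limit, 1.5925/1.4075 = 1.13 (1.08 to 1.20 if the assumed rate ratio is 1.5 to 3).

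With mean 1.5 and gamma shape 1 to 2, the SE of the log rate ratio is √[2(1/1.5 + 1/shape)/56] = 0.24 to 0.20. The shift at the 95% limit, log 1.13 = 0.12, is therefore about 0.5 to 0.6 of an SE. The shift at one SD, log 1.065 = 0.063, is under a third of an SE.

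**5. Error rate given a bad draw.** For an imbalance of 0.37 SD, the unadjusted test statistic has mean r × 0.37/0.189 and SD √(1 − r²). Its conditional type I error is 6.3%, 7.9% and 12.9% for r = 0.2, 0.3 and 0.5. Averaged over all allocations it remains 5%.

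**The case against.** The strongest reply is that nothing is invalid here. Under randomisation, chance imbalance is already part of the standard error, and the unconditional error rate is nominal. That stands, and it limits the point to precision and protection against a bad draw. A reader might infer from the imbalance figures that the planned comparison is biased; the documents do not support that.

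A reader might also infer that the plan decided to discard the LSI. It did not say so. Section 9.c leaves the covariates of the count regressions open and excludes none, and no analysis in section 9 has a covariate list. Nor is any baseline table described, so it cannot be inferred that LSI by arm would go unreported. The accurate statement is that no use is specified.

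The prognostic strength is assumed. Section 1.b speaks of criminal activity and gives no association with infractions or segregation in prison. Restricting entry to moderate-to-high risk narrows the range and may weaken any correlation. This also stands, and it makes the upper rows of the tables less likely.

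For the yes/no outcomes, swapping the chi-square for a logistic model would not bring the expected precision. In simulation (2,000 trials per setting, 112 people, control risk about 50% or 27%, slopes 0.3 to 0.7), adjustment raised the variance of the log odds ratio by about 4% to 15%, because the adjusted model targets a conditional odds ratio. Power rose only about 1 to 5 points. This objection is accepted and shapes the fix.

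Other variables known before allocation (diagnosis, demographics, facility) could also be covariates. That is fair. The LSI is singled out because the trial selects on it and its own rationale calls this kind of risk predictive.

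Finally, section 9 says the analyses will not be conclusive. That lowers the stakes without removing them, since section 2.a still sets an effectiveness objective.

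**Conclusion.** The point holds as a minor improvement. A prognostic classification is available before randomisation on everyone, and section 9.c specifies no use of it for the two primary outcomes that lack a baseline. The unadjusted comparisons are valid on average. Adjustment would cut variance by about 1% to 25% for an assumed r of 0.1 to 0.5, and the low end is plausible given the restricted entry range. An imbalance at the 95% limit would move a null rate ratio to about 1.13 if high-risk people have twice the infraction rate, which is roughly half a standard error.

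These figures rest on 56 per arm, on an LSI-outcome association the documents do not give, and on count distributions chosen for illustration. Segregation days were not modelled separately.

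**What to change.** In section 9.c:

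- Pre-specify the screening LSI score as a covariate in the count regressions for infractions and segregation days. Use the risk level instead if only that is retained.
- Name that adjusted regression as the main between-group comparison for the counts, with Mann-Whitney as supporting.
- For the yes/no forms, keep the chi-square and add an LSI-adjusted comparison reported as a standardised (marginal) risk difference, so that the effect measure does not become a conditional odds ratio.
- Tabulate LSI by arm.

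The cost is SAP wording and one degree of freedom (for a score or a two-level category). It needs no new data collection, provided the score or level is kept in the study data. The documents do not confirm this: Appendix A lists only the eligibility determination.
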